6.4.2.2 Definition of Measurable and Non-Measurable Lesions

The guidelines contained here are based on recommendations of the Prostate Cancer Clinical Trials Working Group's 2007 definitions (PCWG2).²⁸

The PCWG2 definitions use modified RECIST criteria.

Measurable lesions are visceral or extranodal lesions that are ≥ 1 cm in one direction. Lymph nodes are measurable lesions if they are ≥ 2 cm in one direction. Tumor in the prostate may also be used as a measurable lesion.

Non-measurable lesions are those lesions that do not meet the size criteria given above. Other non-measurable lesions are cysts, leptomeningeal disease, ascites, pleural/pericardial effusions and lymphangitis cutis/pulmonis.

Bone lesions will not be considered measurable lesions.

All measurable and non-measurable lesions should be measured at Screening and at the defined tumor assessment time points. Extra assessments may be performed, as clinically indicated, if there is a suspicion of progression.

6.4.2.2 Definition of Index/Non-Index Lesions

All measurable lesions, up to a maximum of **five lesions per organ** and **ten lesions in total**, should be identified as *index* lesions to be measured and recorded on the medical record at Screening. The *index* lesions should be representative of all involved organs. In addition, *index* lesions should be selected based on their size (lesions with the longest diameters), their suitability for accurate repeat assessment by imaging techniques, and how representative they are of the patient's tumor burden. At Screening, a sum of the longest diameters for all *index* lesions will be calculated and considered the baseline sum of the longest diameters. Response criteria to be followed are listed below. The baseline sum will be used as the reference point to determine the objective tumor response of the *index* lesions at tumor assessment (TA).

Measurable lesions, other than *index* lesions, and all sites of non-measurable disease, will be identified as *non-index* lesions. *Non-index* lesions will be recorded on the medical record and should be evaluated at the same assessment time points as the *index* lesions. In subsequent assessments, *non-index* lesions will be recorded as "stable or decreased disease", "absent", or "progression".

6.4.3 **Evaluation of Tumor Response Using mRECIST Criteria**

6.4.3.1 Definition of Index Lesion Response Using mRECIST

* Complete Disappearance of all target lesions

Response (CR):

(SD):

* Partial Response At least a 30% decrease in the sum of the LD of target lesions,

taking as reference the baseline sum LD (PR):

* Progressive At least a 20% increase in the sum of the LD of target lesions, Disease (PD):

taking as reference the smallest sum LD recorded since the

treatment started or the appearance of one or more new

lesions

* Stable Disease Neither sufficient shrinkage to qualify for PR nor sufficient

increase to qualify for PD, taking as reference the smallest sum

LD since the treatment started

6.4.3.2 Definition of Non -Index Lesion Response Using mRECIST

* Complete Disappearance of all non-target lesions and normalization of tumor marker level. Must be confirmed by a scan done within Response (CR):

4-12 weeks after the first scan.

* Incomplete Response/Stable Persistence of one or more non-target lesion(s) or/and maintenance of tumor marker level above the normal limits

Disease (SD):

* Progressive Appearance of one or more new lesions and/or unequivocal

Disease (PD): progression of existing non-target lesions*

Evaluation of Bone Lesions:

For bone lesions, a minimum of two new lesions must be seen on bone scan to be determined progression of disease. Any lesion on bone scan suspected to be flare or inflammation, another study (such as CT or MRI scan) should be done to document the

^{*}Although a clear progression of "non target" lesions only is exceptional, in such circumstances, the opinion of the treating physician should prevail and the progression status should be confirmed later on by the review panel (or study chair).

presence of a new lesion. Bone scan interpretation will follow PCWG2 recommendations.

6.4.3.3 Determination of Overall Response Using mRECIST

Overall Response (OR) is determined as the combination of assessments of *index* and *non-index* lesions using the following criteria:

non mack resions using the following criteria.								
Index Lesion	Non-Index Lesion	New Lesions	Overall Response					
Assessment	Assessment							
CR	CR	No	CR					
CR	SD	No	PR					
PR	CR or SD	No	PR					
SD	CR or SD	No	SD					
PD	Any	Yes or No	PD					
Any	PD	Yes or No	PD					
Any	Any	Yes	PD					

Best OR is the best confirmed response designation over the study as a whole, recorded between the date of first dose until the last tumor assessment for the individual patient in the study. The assessment of response will be at 6 months or sooner if progression is suspected. For the assessment of best OR, all available assessments per patient are considered. **CR or PR determinations included in the best OR assessment must be confirmed by a second (confirmatory) evaluation meeting the criteria for response and performed no less than 4 weeks after the criteria for response are first met.** It may be done between 4 and 12 weeks after the first scan that showed a response.

Imaging of the chest, abdomen and pelvis is required at screening (i.e., baseline) and at each tumor assessment visit, regardless of the location of known metastases. Specifically, a CT scan of the chest, abdomen and pelvis will be done at baseline, 12 weeks, and every 12 weeks while on the study. Similar methods of tumor assessment and similar techniques must be used to characterize each identified and reported lesion at screening

and during subsequent tumor assessments. Imaging-based evaluation is preferred to clinical examination.

If progressive disease is assessed based only on a new lesion(s) found on bone scans, additional imaging studies of the lesion(s) should be performed to confirm the malignant nature of the new findings on the bone scan. Increased intensity of uptake in previously abnormal areas on bone scans is not considered progressive disease, unless the lesions seen on the correlative imaging studies performed of this area meet the criteria for progression. New areas of abnormal uptake on a bone scan represent progressive disease.

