3.5 End of Treatment Cycles

Patients who progress radiographically on ipilimumab after completion of the initial four doses will not receive more immunotherapy once progression has been documented. For soft-tissue lesions, the RECIST criteria for progression (see 6.4.2) will be used. For bone lesions, there should be ≥ 2 new lesions confirmed on a second scan at least 4 weeks later. Progression will not be assessed until completion of the initial 4 cycles of treatment in order to avoid premature discontinuation of therapy.

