5.1.4 Discontinuation of Study Therapy

Subjects MUST be discontinued from study therapy AND withdrawn from the study for the following reasons:

- Withdrawal of informed consent (subject's decision to withdraw for any reason)
- Any clinical adverse event, laboratory abnormality or intercurrent illness which, in the opinion of the investigator, indicates that continued treatment with study therapy is not in the best interest of the subject
- Termination of the study by Bristol-Myers Squibb (BMS).
- Imprisonment or the compulsory detention for treatment of either a psychiatric or physical (e.g., infectious disease) illness.
- Progression of disease, as defined by radiographic progression, **after 12 weeks of therapy**. Furthermore, all radiographic progression must be confirmed by a repeat scan done at least 4 weeks after the suspicious scan. Immune response is not a part of this algorithm.

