8.5 Statistical Analysis Plan

Demographic and clinical characteristics will be summarized using descriptive statistics (e.g. proportions, mean, standard deviation, median, range). The proportion of patients who achieve an undetectable PSA (≤ 0.2 ng/ml) after initiation of ipilimumab therapy will be provided with the exact 95% confidence interval. The Kaplan-Meier method will be used to estimate time to PSA progression, time to disease progression by any measure and time to death from any cause. In evaluation of time to PSA progression and time to disease progression by any measure will be censored for:

- 1) lost to follow-up at the date of last contact
- 2) use of additional cancer therapies that would interfere with ascertainment of the endpoint of interest
- death from a causes other than prostate cancer or treatment of prostate cancer.

Evaluation of time to death will be censored for lost to follow-up at last contact.

The effects of IRAEs and other immune parameters (e.g., a ratio of T regulatory cells to T effector cells) on clinical outcomes will be evaluated using logistic regression for binary endpoints (e.g., achievement of undetectable PSA) and Cox regression for the time to event outcomes (e.g., time to PSA progression).

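### One new bone lesion shown to be malignant is progressive disease under Section 6.4.3.3 but not under Sections 6.4.3.2 and 3.5, and the sections also disagree on confirmation by a repeat scan

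*Combined protocol and SAP*

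**What the plan says.** The combined protocol and SAP states what counts as progression in bone in several places.

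- **Section 3.5 (end of treatment):** "For bone lesions, there should be ≥ 2 new lesions confirmed on a second scan at least 4 weeks later".
- **Section 5.1.4 (discontinuation and withdrawal):** "all radiographic progression must be confirmed by a repeat scan done at least 4 weeks after the suspicious scan". No number of lesions is given.
- **Section 6.4.3.1 (index lesions):** progressive disease includes the appearance of a single new lesion, with no exception for bone.
- **Section 6.4.3.2 (non-index lesions):** the general line begins "Appearance of one or more new lesions and/or unequivocal", again with no exception for bone. The bone paragraph that follows says "a minimum of two new lesions must be seen on bone scan to be determined progression of disease", asks for another study where flare or inflammation is suspected, and adds "Bone scan interpretation will follow PCWG2 recommendations".
- **Section 6.4.3.3 (overall response):** the last row of the table gives progressive disease whenever a new lesion is present, whatever the index and non-index assessments. The closing paragraph says "If progressive disease is assessed based only on a new lesion(s) found on bone scans, additional imaging studies of the lesion(s) should be performed", in order to show that the finding is malignant. It excludes mere brightening of old areas unless correlative imaging meets the criteria for progression, and it ends "New areas of abnormal uptake on a bone scan represent progressive disease".

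No section says which of these prevails.

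**The concern.** Sections 6.4.3.2 and 6.4.3.3 are consecutive steps of one mRECIST assessment, yet they set different thresholds for the same bone scan. The result feeds two secondary analyses. One is response by modified RECIST: bone lesions are not measurable, but a new one can turn overall response into progressive disease. The other is time to progression. Section 8.5 says "The Kaplan-Meier method will be used to estimate time to PSA progression, time to disease progression by any measure", but it does not say which bone rule defines the event.

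The same term also controls conduct. Maintenance dosing from week 24 depends on the absence of radiographic progression (synopsis, Section 5). Withdrawal depends on it (Section 5.1.4). Scans and PSA measurements run until it occurs (Section 3.6 and the footnotes to the schedule in Section 6.1). Two sites are open, and each could in good faith follow a different section. Because a call of progression can end scanning, the data needed to apply the other reading later may not exist.

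**Working it through.** The plan gives no figure to reproduce and no formula applies. The check is to apply each rule to the same scans, assuming no progression by soft tissue or PSA.

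| Scan finding | 3.5 | 5.1.4 | 6.4.3.2 bone paragraph | 6.4.3.3 text and table |
|---|---|---|---|---|
| (a) One new lesion, malignant on further imaging, no repeat scan | No | Not confirmed | No | Progressive disease |
| (b) As (a), and still present on a repeat scan at least 4 weeks later | No | Confirmed, but no lesion count to apply | No | Progressive disease |
| (c) Two or more new lesions, malignant on further imaging, no repeat scan | No | Not confirmed | Yes | Progressive disease |
| (d) As (c), and confirmed at least 4 weeks later | Yes | Yes | Yes | Progressive disease |

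Four things follow.

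1. **Lesion count.** In (a) and (b), 6.4.3.3 conflicts with both 6.4.3.2 and 3.5. The further imaging requested in 6.4.3.3 does not remove the conflict, because it tests what the lesion is, not how many there are.
2. **Confirmation.** In (c), 3.5 and 5.1.4 require a repeat scan, whereas 6.4.3.2 and 6.4.3.3 classify without one. Sections 3.5 and 6.4.3.2 therefore agree on the count but not on confirmation. The 4-week confirmation in 6.4.3.3 applies to complete and partial responses, not to progression.
3. **Section 5.1.4 does not settle the count.** In (b), a persistent single lesion meets its repeat-scan condition, but whether it was radiographic progression in the first place depends on which other section is read.
4. **The general lines match 6.4.3.3, not the bone paragraph.** The single-new-lesion wording in 6.4.3.1 and in the first part of 6.4.3.2, and the last row of the table, all give progression in (a). Within 6.4.3.2 the specific bone paragraph can reasonably be taken to override the general line. Nothing carries that exception into 6.4.3.3.

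Only (d) is classified the same way everywhere.

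**The case against.** The best defence is that the sections can be harmonised. The closing sentence of 6.4.3.3 uses a plural, 6.4.3.2 defers to PCWG2, and end of treatment has its own rule in 3.5. Part of this stands: intent may well have been uniform. But the same paragraph of 6.4.3.3 allows for progression on one lesion ("If progressive disease is assessed based only on a new lesion(s) found on bone scans, additional imaging studies of the lesion(s) should be performed"), and the table row is met by any new lesion. The PCWG2 sentence stands in 6.4.3.2 only; its content is not restated in the documents and nothing says that it overrides 6.4.3.3. Different purposes could separate 3.5 from the response criteria, but not 6.4.3.2 from 6.4.3.3.

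The defence does succeed against several stronger readings that a reader might infer.

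- *Any new uptake is progression under 6.4.3.3.* The paragraph asks for imaging to establish malignancy and excludes increased intensity in old areas. The conflict is limited to a lesion that passes that check.
- *One new focus on one scan stops treatment.* Sections 3.5 and 5.1.4 both require a repeat scan, and no dose is scheduled between weeks 10 and 24, so a week-12 reading stops no dose at that time. What remains is that the synopsis and Section 5 do not define the radiographic progression on which maintenance depends.
- *Every man with one new focus changes status, and his event date moves by a full scan interval.* He does not change status if the focus proves non-malignant or if he progresses by another route at the same visit. The endpoint counts progression by any measure, scans may be done early, and a repeat scan can follow from 4 weeks, so the shift may be zero or shorter than one interval.
- *The primary result is at risk by definition.* The primary endpoint is a PSA threshold, and the Simon rules count men who reach it. Neither uses the bone rule.

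**Conclusion.** The inconsistency is real and narrow. A single new bone lesion, shown malignant and without other progression, is progressive disease under 6.4.3.3 and not progression under the 6.4.3.2 bone rule or 3.5. Separately, the sections disagree on whether progression needs a repeat scan, and 5.1.4 has no lesion count.

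The effect is on overall response, on time to progression by any measure, and on the meaning of radiographic progression for week-24 maintenance, discontinuation, and the end of scan and PSA follow-up. Its size cannot be stated: the documents give no rate of single new bone lesions, and the shift in event date depends on each man's other findings. The definition of the primary endpoint and the two-stage design (10 then 30 patients) stand as they are.

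The conclusion rests on the text alone and on no assumption about what PCWG2 contains. It takes no position on which bone rule is correct. It should be fixed, because following the plan as written gives two answers for the same scan.

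**What to change.** Reconcile Sections 3.5, 5.1.4, 6.4.3.1, 6.4.3.2 and 6.4.3.3 to one definition of bone progression that states the lesion count and whether, and when, a confirming scan is needed. The choice of rule belongs to the sponsor. Carry it into the new-lesion lines of 6.4.3.1 and 6.4.3.2 and the last row of the overall-response table; changing only the closing sentence of 6.4.3.3 would leave those lines and the confirmation mismatch in conflict. State that the same definition is used for response, for time to progression in Section 8.5, and wherever radiographic progression governs treatment continuation or follow-up.

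Cost: a few text edits in a protocol amendment. No new scans, visits or data are needed.

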6.4.4 Response Endpoints

Ipilimumab is expected to trigger immune-mediated responses, which require activation of the immune system prior to the observation of clinical responses. Such immune activation may take weeks to months to be evident. Some patients may have objective increase of tumor lesions or other disease parameters (based on study indication, i.e., hematologic malignancies) within 12 weeks following start of ipilimumab dosing. Such patients may not have had sufficient time to develop the required immune activation or, in some patients, apparent mRECIST progression may represent infiltration of lymphocytes into the original tumor or blood. In conventional studies, such apparent radiographic progression or relevant laboratory parameter increases during the first 12 weeks of the study would constitute PD and lead to discontinuation of imaging to detect response, thus disregarding the potential for subsequent immune-mediated clinical response. In this study, it may not represent actual tumor progression.

Therefore, patients with tumor progression detected or lack of laboratory parameter response documentation prior to week 12 but without rapid clinical deterioration should continue to be treated with ipilimumab and clinically observed with a stringent imaging schedule to allow detection of a subsequent tumor response. This will improve the overall assessment of the clinical activity or ipilimumab and more likely capture its true potential to induce clinical responses. Investigational Product: IPILIMUMAB

The investigational product is defined as a pharmaceutical form of an active ingredient being tested as a reference in the study, whether blinded or unblinded. In this study, the investigational product is ipilimumab.

Other medications used in the study as support or escape medication for preventative, diagnostic, or therapeutic reasons, as components of the standard of care for a given diagnosis, are considered non-investigational products. In this protocol, there are no non-investigational product(s).

Identification

Ipilimumab is available in 5 mg/mL single-use vials (10 mL or 40 mL). The sterile solution in the vial is clear and colorless. Ipilimumab is administered via intravenous infusion only.

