1.4 Overall Risk/Benefit Assessment melanoma and prostate cancer

Results from the 3 primary efficacy studies of ipilimumab suggest that the 10 mg/kg dose is active and offers the best benefit to risk ratio based on a 27.1% to 35.1% rate of disease control and a favorable 1-year survival rate of 48.6% to 59.1% compared with that reported in the literature (25.5% to 35%). ^{24,25,26,27} Substantial reductions in total tumor burden, including widely disseminated disease in the skin, lung, and/or other visceral

disease sites, were reported. More than half the responses were reported in subjects staged with M1b or M1c advanced melanoma disease, which is most resistant to approved therapies. The kinetics of ipilimumab resulted in known patterns of clinical activity (CR, PR and SD) as well as novel patterns, characterized by reductions in total tumor burden, including existing and new lesions, after initial tumor volume increase and/or after appearance of new lesions. In the pretreated population at 10 mg/kg in 2 of the 3 studies, disease control after initial tumor volume increase and/or new lesions was reported for 9.7% of subjects. Across all 3 studies, stable disease was often accompanied by clinically relevant reductions in tumor burden compared to baseline. All patterns of response, including SD, appeared to result in favorable survival, based on 1-year survival rates.

Characteristic organ-specific inflammatory IRAEs were reported with ipilimumab therapy, typically during induction therapy. IRAEs were mostly reversible within days to weeks following cessation of therapy or treatment with symptomatic therapy, corticosteroids or other anti-inflammatory agents, depending upon severity. Accumulated clinical experience resulted in detailed toxicity management guidelines (also termed algorithms), by use of which IRAEs can be effectively managed, especially when IRAEs are recognized early and subjects are treated in a timely fashion. This can minimize the occurrence of IRAE complications, such as GI perforation/colectomy or hepatic failure.

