2.2 Secondary Objectives

- Time to PSA progression
- Time to progression by any measure
- Maximum percentage of PSA reduction in each patient
- Number of patients with IRAEs and correlation of these with complete PSA response, time to progression, and T cell measurements
- Measures of T cell response to therapy with flow cytometry
- Response in Measurable disease by modified RECIST criteria
- Time to death from any cause.
- To examine correlative biomarkers and their relationship to clinical outcomes. Potential biomarkers include, but are not limited to CRP, IGF-1 and -2, or FSH.
- Bank samples for future molecular correlative studies, biomarker, or other studies.

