6 STUDY PROCEDURES AND OBSERVATIONS

6.1 Time and Events Schedule for Protocol CA184059

		Induction* (Cycles 1-4)			Between Treatments			Maintenance* (Cycles 5-8)			Every 6 Month Follow Up*		
T //P 1	Scree . #	Wk	Wk	Wk	Wk	Wk	Wk	Wk	11/1 24	WI 26	XX/1 40	W/I (0	Evel Fc
Test / Procedure	ning#	1	4	/	10	12	18	23/24	Wk 24	Wk 36	Wk 48	Wk 60	Π
Informed Consent	X												
Inclusion / Exclusion Criteria	X												
Demographics, medical history, concurrent medical conditions	X												
Testosterone level	X												
Serum samples for hepatitis panel and HIV, if high index of suspicion	X												
ECOG performance status	X	X	X	X	X	X	X	X	X	X	X	X	
Blood collection for correlative studies ¹		X	X	X	X								
Physical Exam	X	X	X	X	X	X	X	X	X	X	X	X	
Vital Signs	X	X	X	X	X	X	X	X	X	X	X	X	
Weight		X	X	X	X				X	X	X	X	
Bone Scan ²	X					X		X		X	X	X	
Chest, Abdomen & Pelvis CT ²	X					X		X		X	X	X	

CBC with differential	X	X	X	X	X	X	X	X	X	X	X	X	
Chemistry Panel: Creatinine, BUN, electrolytes (sodium, potassium, chloride), glucose, bilirubin alkaline phosphatase, ALT, AST, calcium, ³	X	X	X	X	X	X	X	Х	Х	X	Х	X	
LDH	X												
Autoimmune Profile: TSH, free T4	X	X	X	X	X				X	X	X	X	
PSA ⁴	X	X	X	X	X	X	X	X	X	X	X	X	
Concurrent medications (include documentation of androgen suppression therapy)	X	X	X	X	X				X	X	X	X	
Adverse Effects Recorded	X	X	X	X	X		_		X	X	X	X	
Ipilimumab		X	X	X	X				X	X	X	X	
Telephone Contact													X

^{*} Cycle 1-8 procedures can be done +/- 3 days and Long Term Follow-Up can be done +/- 2 weeks.

#Screening procedures must be done within 28 days of first treatment

^{**}PSA, Autoimmune profile, LDH, CBC Diff, Chem panel including Creatinine, BUN, electrolytes (sodium, potassium, chloride), glucose, bilirubin, alkaline phosphatase, ALT, AST, calcium, phosphorus and Correlative **baseline samples** DO NOT need to be repeated on Cycle 1 Day 1 if done within 7 Days of Cycle 1 Day 1

¹ Per outlined correlative studies

² Imaging Studies will also be done every three months until radiographic progression

³ Available labs (i.e. chemistries and blood counts) will be reviewed prior to each infusion

⁴ PSA will be done until radiographic progression

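### A persisting early soft-tissue lesion scores PD under the 6.4.3.3 table even when total tumour burden later meets the PR threshold, although 6.4.4 continues imaging to find such responses

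*Combined protocol and SAP*

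**What the plan says.** Section 6.4.4 explains that immune activation may take weeks to months and that apparent mRECIST progression in the first 12 weeks may not be real. Men with such findings and no rapid deterioration "should continue to be treated with ipilimumab and clinically observed with a stringent imaging schedule to allow detection of a subsequent tumor response". Section 3.5 points the same way: "Progression will not be assessed until completion of the initial 4 cycles of treatment in order to avoid premature discontinuation of therapy". Section 1.4 describes reductions in total burden after new lesions appear as a known pattern with this drug.

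The endpoint is listed in section 2.2 as "Response in Measurable disease by modified RECIST criteria". Its scoring rules are these:

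- **Index lesions (6.4.3.1).** PR is a fall of at least 30%, "taking as reference the baseline sum LD". PD is a rise of at least 20%, "taking as reference the smallest sum LD recorded since the" start of treatment, or a new lesion.
- **Overall response (6.4.3.3).** A new lesion gives PD whatever the index and non-index lesions do. Every CR, PR and SD row requires no new lesion.
- **Best response (6.4.3.3).** "Best OR is the best confirmed response designation over the study as a whole". All available assessments count, and CR or PR must be confirmed at least 4 weeks later.
- **Bone.** Section 6.4.3.2 requires at least two new bone-scan lesions for progression. The closing paragraph of 6.4.3.3 gives no minimum number.

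On follow-up, footnote 2 of the section 6.1 schedule reads "Imaging Studies will also be done every three months until radiographic progression". Section 3.6 moves men to telephone surveys after radiographic progression. Section 5.1.4 withdraws men from the study for radiographic progression after 12 weeks, confirmed by a repeat scan at least 4 weeks after the suspicious one.

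**The concern.** The stated purpose of continued imaging and the scoring table do not meet. A man may develop a soft-tissue lesion during induction that then shrinks but stays visible. His total burden can fall by 30% or more, yet each scan that shows the lesion is entered as PD. He is the kind of delayed responder that 6.4.4 wants to capture, and he is counted as a non-responder.

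Two results are at stake. One is the secondary measurable-disease response rate. The other is the comparison in 6.4.2 of objective response with depth of immune response, where such a man would sit in the wrong group. Immune-related response criteria appear in the abbreviation list (Appendix 1), but section 6.4 contains no rule that uses them.

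**Working it through.** The plan states no response rate or expected count for this endpoint, so there is no figure to reproduce. The check applies the written rules to hypothetical lesion sums, with non-index lesions taken as stable.

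**Rules as formulas.** Index PR: sum ≤ 0.70 × baseline. Index PD: sum ≥ 1.20 × smallest earlier sum. Overall: PD if a new lesion is present, otherwise as the table gives.

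**1. New soft-tissue lesion persists.** Baseline index sum 100, then 90, 60, 55, with a new lesion at all three scans.
- Index change from baseline: -10%, -40%, -45%, so SD, PR, PR.
- Overall by the table: PD, PD, PD. The response is not counted.

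**2. Total burden, using only scans that the plan already requires.** Baseline 50 mm. Total including the new lesion is 35 mm at week 12 and 32 mm at the repeat scan at least 4 weeks later. Section 6.4.2.2 sets 1 cm as the limit for a measurable visceral or extranodal lesion. With the new lesion at 10 mm both times, the index sums are 35 - 10 = 25 mm and 32 - 10 = 22 mm.
- Total change: 35/50 - 1 = -30%; 32/50 - 1 = -36%. Both meet the PR threshold, and the second confirms the first.
- Overall by the table: PD, PD.

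**3. A longer record, if imaging continues.**

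| Week | Index sum (mm) | New lesion (mm) | Total (mm) | Total vs baseline | Table |
|---|---|---|---|---|---|
| 0 | 50 | – | 50 | – | – |
| 12 | 48 | 12 | 60 | +20% | PD |
| 16 | 42 | 10 | 52 | +4% | PD |
| 24 | 30 | 5 | 35 | -30% | PD |
| 36 | 26 | 4 | 30 | -40% | PD |
| 48 | 25 | 4 | 29 | -42% | PD |

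On total burden this man has a PR at week 24, confirmed at week 36. Under the table he has PD at all five scans. This record needs scans after week 16, which sections 3.6, 5.1.4 and 6.1 put in doubt.

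**4. New lesion disappears.** Index sums as in step 1, with the new lesion at the first scan only.
- Scored scan by scan: PD, PR, PR, a confirmed PR if the last two scans are at least 4 weeks apart.
- New-lesion entry carried forward: PD, PD, PD.

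The documents do not say which applies.

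**5. Index growth without a new lesion.** Sums 50, 70, 62, 55, 34, 33 mm at weeks 0, 12, 16, 24, 36, 48.
- Change from baseline: +40%, +24%, +10%, -32%, -34%.
- Smallest earlier sum at each scan: 50, 50, 50, 50, 34. The growth to 70 mm never enters it.
- Score: PD, PD, SD, PR, PR. Best response is a confirmed PR.

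Early growth raises the bar but does not close the route. After growth of a fraction g, the shrinkage from peak needed for PR is 1 - 0.70/(1 + g), here 1 - 0.70/1.40 = 50%. If the screening scan is left out of the PD reference, 70 mm serves as the reference at week 16, which only makes PD harder to reach.

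**The case against.** Strict modified RECIST is a prespecified and legitimate choice, and 6.4.4 can be read as guidance on treating and imaging rather than scoring. Its operative sentence covers progression before week 12, while the first scheduled on-treatment scan is at week 12. If imaging ends at confirmed progression, a new scoring rule cannot recover scans that were never taken. The endpoint is secondary, is absent from the list in 8.2, and has no analysis specified in 8.5.

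Much of this stands. It is a reason to keep strict mRECIST as the main classification, and it limits the importance of the point. It does not remove the gap. Section 6.4.4 is headed as a section on response endpoints and gives detection of later response as its aim. A lesion first seen at the week-12 scan appeared during the period that the section describes. Step 2 shows a response lost from two scans that the plan requires, so the change gains something even if imaging then stops.

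Three stronger readings are tempting, and the documents do not support them:

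- **Any early growth bars a later response, or is absorbed into the PD reference.** The reference is a minimum, PR is measured from baseline, and best response uses all assessments. Step 5 ends in a confirmed PR and is lost only if imaging ends first.
- **Any new lesion scores PD at every later scan.** Section 6.4.3.2 requires two new lesions in bone, and carry-forward is not stated.
- **The frequency can be taken from section 1.4, where "disease control after initial tumor volume increase and/or new lesions was reported for 9.7% of subjects".** That figure is from pretreated melanoma, is disease control rather than response, and pools volume increase with new lesions. It does not measure response with a persisting new lesion in this population.

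**Conclusion.** The point holds for new soft-tissue lesions. While an early lesion remains visible, the 6.4.3.3 table gives PD even when total burden has fallen by 30% or more. Where the lesion disappears, the score depends on a rule that the plan does not state. Index growth without new lesions is scored adequately, provided that the scans are taken.

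The direction of the error is downward: delayed responders of this type are counted as PD, never the reverse. Its size cannot be given. The documents provide neither the number of men with measurable disease nor a rate for this pattern in prostate cancer. The lesion sums above are illustrations of the rules, not estimates.

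The effect is confined to the secondary measurable-disease response and the comparison with immune response. A reader might infer that the trial's success rule is at risk. It is not: the rule of 6 or more of 30 men rests on PSA alone.

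**What to change.** 1. In 6.4.3.3, state that the new-lesion entry is scored scan by scan, so that it clears when the lesion is gone.
2. Beside the strict mRECIST result, report a supplementary best overall response. Measurable soft-tissue lesions first seen up to and including the week-12 scan are added to the sum of longest diameters, and stay in it at later scans. PR and CR are judged on that total against baseline, with the existing confirmation rule. New bone lesions stay under 6.4.3.2. State also how a new soft-tissue lesion below the 6.4.2.2 size limits is handled. Recording it as non-index, so that it rules out CR while visible but is not PD by its appearance alone, would fit the present structure.
3. Give the comparison of objective response with immune response under both classifications.
4. Reconcile 6.4.4 with 3.6, 5.1.4 and footnote 2 of 6.1 on whether imaging continues after apparent early progression. Reconcile 6.4.3.2 with the closing paragraph of 6.4.3.3 on the number of new bone lesions. No treatment rule is proposed here.

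The cost is protocol wording and one derived variable. Section 6.4.2.2 already requires all lesions to be measured at each tumour assessment. The supplementary rate will not be comparable with historical RECIST rates, which is why the strict result stays beside it.
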